4 OBJECTIVES AND ENDPOINTS

Study objectives and specific endpoints are listed in [Table 3](#). Additional endpoints and analyses will be described in the statistical analysis plan (SAP), the Endoscopy Image Review Charter [REDACTED]. Selected efficacy endpoints are further defined in [Table 10](#).

Table 3: Study Objectives and Endpoints

Objective	Endpoints
Primary - Efficacy	

To estimate the efficacy of BMS-986165 at Week 12	
Proportion of subjects in clinical response at Week 12
Safety	

To assess the safety and tolerability of BMS-986165	
Number and proportion of subjects experiencing AEs, SAEs, AEs leading to discontinuation from the study, and AEIs throughout the study
Exploratory - Efficacy	
[REDACTED]	

Table 3: Study Objectives and Endpoints

Objective	Endpoints

 To explore the efficacy of BMS-986165 at Week 52 	
 Proportion of subjects in clinical remission at Week 52 Proportion of subjects in clinical response at Week 52 Proportion of subjects in endoscopic remission at Week 52 Proportion of subjects with endoscopic improvement at Week 52 Proportion of subjects with histologic improvement at Week 52 Proportion of subjects with corticosteroid-free remission at Week 52 Proportion of subjects in durable clinical response at Week 52 Proportion of subjects in durable endoscopic response at Week 52 Proportion of subjects in clinical response at Week 12
Exploratory	

 To explore the effect of BMS-986165 on PB immune cells 	
 Change from baseline in PB immune cells over time

 To explore the effect of BMS-986165 on the transcriptome in blood and colon biopsies 	
 Change from baseline in gene expression over time
Exploratory	
Exploratory - Health-related Quality of Life and Medical Resource Utilization	

 To explore the effect of BMS-986165 on PROs and quality of life 	
 Change from baseline at various time points for the IBDQ

Table 3: Study Objectives and Endpoints

Objective	Endpoints

 To explore the effect of BMS-986165 on UC-related hospitalization and surgery 	
 Proportion of subjects with surgery and/or hospitalization due to UC at various time points

AE = adverse event; AEI = adverse event of interest; IBDQ = Inflammatory Bowel Disease Questionnaire; PB = peripheral blood; [REDACTED] PRO = patient-reported outcomes; RB = rectal bleeding; [REDACTED] SAE = serious adverse event; [REDACTED] SF = stool frequency; UC = ulcerative colitis; [REDACTED]

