 - Subjects who have completed screening procedures (up to 28 days duration) and met Inclusion/Exclusion criteria will be randomized on Day 1 of the treatment period.
 - **Not Applicable to Subjects Enrolled Under Protocol Amendment 02.** Subjects will be randomized in a 3:1:1 ratio using interactive response technology (IRT) to receive oral BMS-986165 12 mg BID, BMS-986165 6 mg BID, or placebo BID during the 12-week treatment period.
 - Subjects will be randomized in a 3:1 ratio using IRT to receive oral BMS-986165 12 mg BID or placebo BID during the 12-week treatment period.
 - Subjects randomized to the BMS-986165 6 mg BID arm under the Original Protocol or Protocol Amendment 01 will continue to receive BMS-986165 6 mg BID for the 12-week double-blind treatment period.
 - Randomization will not be stratified.

- **Study periods:**
 - Screening: up to 4 weeks (28 days)
 - Double-blind treatment: 12 weeks (84 days)
 - OLE: up to 40 weeks (280 days)
 - Follow-up: 4 weeks (28 days)

The total duration of study participation is approximately 60 weeks (420 days) in 4 periods.

- **Study assessments:** Include assessments of medical and UC disease history, prior medications, concomitant medications and UC medications, tobacco use, baseline SF; physical examinations; chest x-ray (CXR); 12-lead electrocardiogram (ECG); blood, stool, and urine sample collections; endoscopies with biopsies; additional efficacy assessments and the Physician's Global Assessment (PGA); and subject collection of PROs in daily electronic diaries as outlined in the Schedule of Activities ([Section 2](#)).

- **Discontinuation from the study:** Subjects who discontinue study treatment will remain in the study and are required to continue to be followed for protocol-specified post-treatment follow-up procedures. The only exception to this is when a subject specifically withdraws consent for any further contact with him/her or persons previously authorized by the subject to provide this information.

Safety monitoring will occur at study sites, by the Sponsor, and also by an external, independent DMC ([Section 5.1.6](#)).

Number of Subjects: Approximately 50 subjects

Treatment Arms and Duration:

Double-blind Treatment Period: On Day 1, subjects will be randomized to receive 1 of the following study treatments:

- BMS-986165 12 mg BID
- **Not Applicable to Subjects Enrolled Under Protocol Amendment 02.** BMS-986165 6 mg BID
- Placebo BID

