8 DISCONTINUATION CRITERIA

8.1 Discontinuation from Study Treatment

Subjects MUST discontinue IP (and non-IP at the discretion of the investigator) for any of the following reasons:

- Subject's request to stop study treatment. Subjects who request to discontinue study treatment will remain in the study and must continue to be followed for protocol-specified posttreatment follow-up procedures ([Section 5.1.4](#)). The only exception to this is when a subject specifically withdraws consent for any further contact with him/her or persons previously authorized by subject to provide this information.
- Any clinical AE, laboratory abnormality, or intercurrent illness which, in the opinion of the investigator, indicates that continued participation in the study is not in the best interest of the subject

- Termination of the study by BMS
- Loss of ability to freely provide consent through imprisonment or involuntarily incarceration for treatment of either a psychiatric or physical (eg, infectious disease) illness. (Note: Under specific circumstances and only in countries where local regulations permit, a participant who has been imprisoned may be permitted to continue as a participant. Strict conditions apply and BMS approval is required).
- Subject meets 1 of the following criteria for laboratory abnormalities in 2 sequential laboratory measurements taken 3 to 5 days apart:

- [REDACTED]
- [REDACTED]
- [REDACTED]
- [REDACTED]
- [REDACTED]
- [REDACTED]
- [REDACTED]
- [REDACTED]

- Subject meets any of the following criteria for liver-related laboratory abnormalities. If these abnormalities are identified, repeat testing should occur within 48-72 hours and these results should be discussed with the BMS Medical Monitor/designee. Additional recommendations on the recognition and investigation of potential DILI are given in [Section 9.2.7](#).
 - ALT or AST > 8 × ULN on a single occasion
 - ALT or AST > 5 × ULN for more than 2 weeks
 - ALT or AST > 3 × ULN **and** total bilirubin > 2 × ULN **or** international normalized ratio (INR) > 1.5
 - ALT or AST > 3 × ULN with the appearance of fatigue, nausea, vomiting, right upper quadrant pain or tenderness, fever, rash, and/or eosinophilia (> 5%)

- [REDACTED]
- [REDACTED]

- Unblinding of a subject’s treatment assignment for any reason (emergency or nonemergency)
- Inability or failure to comply with protocol requirements

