8.2 Discontinuation from the Study

Subjects who request to discontinue study treatment ([Section 8.1](#)) will remain in the study and continue to be followed for protocol-specified posttreatment follow-up procedures. The only exception to this is when a subject specifically withdraws consent for any further contact with him/her or persons previously authorized by subject to provide this information.

- Subjects should notify the investigator of the decision to withdraw consent from future follow-up **in writing**, whenever possible.
- The withdrawal of consent should be explained in detail in the medical records by the investigator and entered on the appropriate eCRF page.
- In the event that vital status (whether the subject is alive or dead) is being measured, publicly available information should be used to determine vital status only as appropriately directed in accordance with local law.
- If the subject withdraws consent for disclosure of future information, the Sponsor may retain and continue to use any data collected before such a withdrawal of consent.

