9.2.8 Adverse Events of Interest (Clinical Safety Program)

All AEs and SAEs that arise in the study will be reported and investigated. However, because of the characteristics of the disease under study, and BMS-986165 in particular, some AEs are considered adverse events of interest (AEIs). AEIs may be serious or nonserious. Such events may require further investigation to better characterize and understand them.

In addition, given that immunosuppression is consistent with the mechanism of action of BMS-986165, malignancies are considered to be an important potential risk of therapy with BMS-986165 and will be monitored as AEs. Malignancies were not identified as adverse findings in nonclinical studies and no serious adverse reactions of malignancy have been reported to date in clinical studies of BMS-986165.

Additional information on AEs will be collected in this study. Reporting of an AE or SAE that includes a PT that is linked to an AEI will trigger specialized eCRF pages to collect additional information related to characterization, social/family history, risk factors, signs/symptoms, diagnostics, and treatments. Additional information may also be requested to aid in the evaluation of these AEs.

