10.3 Endpoints

Study endpoints are defined in [Section 4](#).

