10.4.1.1 Primary Endpoint

Analysis Method:

The proportion of subjects achieving clinical response at Week 12 and the associated 95% CI for the BMS-986165 12 mg BID treatment arm will be estimated using the Clopper-Pearson exact method. Supportive analysis using logistic regression for the clinical response (binary endpoint) may be performed, and the odds ratio between treatment groups and the corresponding 95% CI may be provided if the data are sufficient to do so.

Imputation Method:

Occurrence of intercurrent events may have an impact on the estimand of interest for the following types of subjects: (1) subjects who discontinue treatment or study early (ie, prior to Week 12); (2) subjects who start a protocol prohibited medication/therapy; or (3) subjects who are lost to follow-up or have otherwise missing endpoint data at or prior to the Week 12 assessment. In these cases, the primary endpoint will be determined using the “Composite Strategy” as defined in the International Council for Harmonisation (ICH) E9 (R1) addendum and will be considered a measure of nonresponse to treatment.⁵⁸ Subjects with the identified intercurrent event(s) will have their clinical response endpoint imputed as being a “nonresponder.” This is commonly known as nonresponder imputation.

Sensitivity analyses using different imputation methods may be performed and will be defined in the SAP.

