10.4.2.1 Adverse Events

Treatment-emergent AEs (TEAEs) are defined as AEs that occur after the subject received first dose of study treatment or if a preexisting condition worsens in severity or becomes serious after receiving the first dose of study treatment up to 30 days after the last dose of study treatment. All reported TEAEs, SAEs, deaths, AEs leading to study treatment discontinuation, and target AEs will be summarized by the Medical Dictionary for Regulatory Activities (MedDRA) SOC and PT.

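### Does the safety endpoint in Table 3 name different events from those Section 10.4.2.1 will tabulate?

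*Combined protocol and SAP*

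**What the plan says.** Table 3 in Section 4, and the Synopsis in the same words, give the safety endpoint as the number and proportion of subjects with AEs, SAEs, "AEs leading to discontinuation from the study, and AEIs throughout the study". Section 10.3 adds no definition of its own: "Study endpoints are defined in" Section 4. Section 10.4.2.1 then lists what will be shown by system organ class and preferred term: TEAEs, SAEs and deaths, after which it says that "AEs leading to study treatment discontinuation, and target AEs will be summarized".

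Elsewhere the protocol separates stopping drug from leaving the study. The Synopsis says: "Subjects who discontinue study treatment will remain in the study and are required to continue to be followed". Section 8.1 says: "Subjects who request to discontinue study treatment will remain in the study and must continue to be followed". Section 8.2 repeats that such subjects "will remain in the study and continue to be followed for protocol-specified posttreatment follow-up procedures". Section 10.4.1.1 lists "subjects who discontinue treatment or study early" as one group with an intercurrent event, which names the two as alternatives.

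Section 10.4.2 makes the safety analyses descriptive and asks for summaries by period as well as combined. Table 16 groups the Safety Analysis Set by treatment received. Section 5.1.3 puts every subject in the open-label extension (OLE) on 6 mg BID.

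**The concern.** Because Section 10.3 sends the reader back to Section 4, the Table 3 wording appears to govern. Its discontinuation component echoes the title of Section 8.2 (leaving the study), while Section 10.4.2.1 analyses the event in Section 8.1 (stopping drug). If a subject who stops drug for an AE normally stays in follow-up, the endpoint as worded could miss that subject.

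The AEIs of Table 3 and Section 9.2.8 also reappear as 'target AEs' in Section 10.4.2.1, a term found nowhere else in the visible text, and as AEs of special interest in Sections 5.1.6 and 9.2.3.

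This is the first use of 12 mg BID in ulcerative colitis, and Section 3.2 says that its tolerability may inform the Phase 3 dose. An understated rate of intolerance, or an unclear set of events of interest, would therefore matter. A lesser worry is the combined-period table: if subjects kept their randomised label there, much of the time shown under 12 mg or placebo would be time on 6 mg.

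**Working it through.** **1. The plan's own safety figure.** Section 10.1.2 gives the chance of seeing at least one case of an AE among 37 subjects. The formula is 1 − (1 − p)^37.
- p = 10%: 1 − 0.90^37 = 0.980 (plan: 98%).
- p = 6%: 1 − 0.94^37 = 0.899 (plan: 90%).

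Both reproduce, and neither depends on the wording in question.

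**2. The components side by side.**

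| Declared in Table 3 | Summarised in Section 10.4.2.1 | Match |
|---|---|---|
| AEs | TEAEs | yes |
| SAEs | SAEs, deaths | yes |
| AEs leading to study discontinuation | AEs leading to treatment discontinuation | term differs |
| AEIs | target AEs | label differs |

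**3. What would be at stake if the terms meant different events.** Assume, purely for illustration, that 4 of 37 subjects on 12 mg stop drug for an AE: 4/37 = 10.8% (Clopper-Pearson 95% CI 3.0 to 25.4). If none of them also left the study, a literal endpoint would read 0/37 = 0% (0 to 9.5). The documents give no such counts. The 10.8% figure would be reported in any case, because it is the table Section 10.4.2.1 already plans.

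**4. Which event Table 3 means.** The protocol uses the two terms loosely.
- The Section 8.1 rule that stops drug for an AE is phrased as a judgement on whether staying in the study serves the subject.
- The Synopsis item headed as discontinuation from the study, and Section 8.2, both open with subjects who stop treatment.
- Section 8.1.1, on interrupting drug in the OLE, refers to AEs that fall short of study discontinuation criteria.
- Section 8.2 gives no AE-based reason to leave the study.

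The one AE-driven discontinuation rule is therefore Section 8.1. The literal reading gives an endpoint that is almost empty by design, which is a sign that it was not intended.

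**5. How far the two events differ in practice.** A subject who stops drug for good has an early termination visit (Sections 5.1.2 and 5.1.3) and then 4 weeks of follow-up (Sections 5.1.4 and 8.1.2), not visits to Week 52. The reason for stopping treatment goes on the eCRF (Section 8.1), and so does any withdrawal of consent (Section 8.2).

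**6. The labels for events of interest.** Section 9.2.3 uses AEs of special interest and points to Section 9.2.8 for the definition, where the term is AEI. Those two labels are thus one set, and only 'target AEs' lacks a link. Section 5.1.6 cites Section 9.2.8 for skin events, yet the visible text of Section 9.2.8 does not mention skin, so part of it appears to be redacted. The visible text cannot show that the term is undefined.

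**7. The combined-period table.** Let e be the share of subjects who enter and complete the OLE, with all subjects completing 12 weeks. The OLE share of person-time is 40e/(12 + 40e).
- e = 1: 40/52 = 76.9%.
- e = 0.5: 20/32 = 62.5%.
- e = 0.25: 10/22 = 45.5%.

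The values of e are assumed. The shares would mislead only if randomised labels were kept, whereas Table 16 groups by treatment received. The comparison of 12 mg with placebo comes from the separate double-blind summary, which contains no OLE time.

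**The case for a change.** The strongest case is that Table 3 is protocol text. A SAP can specify an analysis but leaves the declared endpoint as it stands, and safety is the only objective besides the primary that is not exploratory. Discontinuation for AEs is a central measure of tolerability, and the comparison with Study IM011024 that Section 3.2 foresees needs one definition. Loose usage elsewhere, on this view, is a reason to align the terms and does not settle which event is counted.

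Part of this stands. The two sections do use different words, and nothing visible links 'target AEs' to Section 9.2.8. Table 16 also does not say how OLE events are attributed in a combined display.

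The claim that the endpoint would go wrong does not stand. The informative count, drug stopped for an AE, is in the planned output whatever Table 3 calls it. Nor is withdrawal of consent for further contact the only exception to follow-up: Section 8.1 also names loss of the ability to consent freely. Neither exception turns an ordinary AE-driven drug stop into a study exit. Attribution in a combined table, and whether to adjust for exposure, are details that Sections 4 and 10.4 leave to the SAP.

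**Conclusion.** No change to the plan is needed. The mismatch is a clerical one in two of the four components of a descriptive endpoint, and its effect on planned results and stated figures is nil. An analyst following Section 10.4.2.1 would report the 12 mg subjects who stopped drug for an AE, in a double-blind summary set against placebo, and that is what a judgement of tolerability requires.

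This rests on two readings. The first is that Table 3 means discontinuation of study treatment, which Section 8.1 supports. If exits from the study were also wanted, the recorded reasons for stopping drug and for withdrawing consent would let an analyst derive them. The second is that 'target AEs' means the AEIs of Section 9.2.8, which is plausible but cannot be confirmed from the visible text. The combined-period layout is a gap that analysts fill sensibly, since Table 16 already points to treatment received.

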5 STUDY DESIGN

5.1 Overall Design

Study IM011127 is a Phase 2 randomized, double-blind, placebo-controlled, multicenter clinical study designed to assess the safety and tolerability, efficacy, [REDACTED] and biomarker response of BMS-986165 12 mg BID in subjects with moderate to severe UC. The primary objective is to estimate the effect of BMS-986165 on clinical response at Week 12 (Table 10).

The duration of study participation is approximately 60 weeks (420 days) in 4 periods, as follows:

[figure not shown]
- Screening period: up to 4 weeks (28 days; Section 5.1.1)
- Double-blind treatment period: 12 weeks (84 days; Section 5.1.2)
- OLE period: up to 40 weeks (280 days; Section 5.1.3)
- Posttreatment follow-up period: 4 weeks (28 days; Section 5.1.4)

Assessments of medical and UC disease history; prior medications, concomitant medications, and UC medications; tobacco use; baseline SF; physical examinations; chest x-ray (CXR); 12-lead ECG; and blood, stool, and urine sample collections; endoscopies with biopsies; additional efficacy assessments, PGA, PROs; and eligibility assessment will be performed as indicated in the Schedule of Activities (Section 2). Subjects will be closely monitored for AEs throughout the study.

The primary endpoint of this study is the proportion of subjects in clinical response at Week 12. This is assessed using the modified Mayo score. This instrument utilizes data from 2 sources: (1) PROs, ie, SF and RB captured by the subject in their electronic daily diary (modified Mayo score and total Mayo score); and (2) Centrally-read endoscopic assessments (modified Mayo score and total Mayo score). In addition, the physician-reported PGA, assessed by the investigator or designee at each study visit, will also be captured to facilitate the calculation of the total and partial Mayo scores. Efficacy will also be assessed using additional instruments, such as the UC-100 instrument (which uses the modified Mayo score SF and ES subscores [REDACTED]). Consequently, accurate and timely collection of each of these types of data (or samples that contribute to these data) is critical to the assessment of efficacy in this study. Additional detail on data capture for efficacy assessment and the efficacy instruments used in this study are given in Section 9.1.1.

Subjects will receive and be trained on the electronic daily diary at the screening visit. Subjects are expected to complete this diary on a daily basis throughout their participation in the study. In order to confirm that subjects are successfully recording data in the electronic daily diary, sites should review subject compliance with completion of the electronic daily diary, as indicated in the Schedule of Activities ([Section 2](#)), or more frequently if required. For the purpose of eligibility assessment and efficacy analysis, the **3 most recent (not necessarily consecutive), valid, electronic subject diary entries recorded from the 7 days prior to the day of a study visit (or up to the day before a subject starts bowel preparation for an endoscopy, if that visit includes an endoscopy)** will be used to calculate the SF and RB subscores (see [APPENDIX 9](#)). Electronic diary entries for SF and RB are considered valid when no medications for constipation, diarrhea, or bowel irregularity are reported (through E-diary) as taken that day. Review of electronic daily diary compliance during these previsit (or preendoscopy) periods is recommended. Subjects are not eligible to participate in this study if they are unable to complete study procedures, which includes daily completion of the electronic diary. The modified Mayo score calculated to determine eligibility will also be used as the baseline disease activity score.

Endoscopic evaluations and collection of colonic tissue biopsies will be performed during the screening period, at Weeks 12 and 52, at unscheduled visits (if clinically indicated), and at early termination (ET) visits that occur at least 4 weeks after the last per protocol-required endoscopy in the double-blind period and any time after Week 20 in the OLE period. Endoscopy is encouraged in subjects terminating in the OLE period between Week 12 and Week 20. Endoscopic procedures will be video recorded and scored for disease activity by a blinded central reader. Histologic scoring of gastrointestinal tissue specimens will also be performed by a blinded central reader.

[figure not shown]

Subjects who meet the criteria for treatment failure will permanently discontinue IP and enter the posttreatment follow-up period ([Section 5.1.3](#)).

An independent Data Monitoring Committee (DMC) will be instituted to assess safety data ([Section 5.1.6](#)).

The study design schematic is presented in [Figure 1](#).

Figure 1: Study Design Schematic

BID = twice daily; OLE = open-label extension; PO = orally; R = randomization

Note: Subjects randomized to the BMS-986165 6 mg BID induction treatment arm under the Original Protocol or Protocol Amendment 01 will continue to receive this dose throughout the double-blind period and will receive 6 mg BID in the OLE period.

